**Table 3c: Adjuvant Treatment of non pCR Patients**

Product	Dose	Dose Frequency	Route of Administration	Appearance	Storage Conditions (per label)
Dabrafenib	150 mg	BID	By mouth	Capsules for oral use	Refer to Associated IB

Trametinib	2mg	Daily	By mouth	Tablets for oral use	Refer to Associated IB
Spartalizumab	400mg	Every 28 days	Intravenous	Liquid in vial for infusion	Refer to Associated IB

### 3.3.1 Dose Selection Rationale

The dose of dabrafenib is 150mg BID which is the FDA approved dose for patients with unresectable or metastatic melanoma with BRAF V600E or V600K mutations.

The dose of trametinib is 2mg daily, which is the FDA, approved dose for patients with unresectable or metastatic melanoma with BRAF V600E or V600K mutations.

The dose of spartalizumab is 400mg every 28 days, administered as an intravenous infusion. In study [CPDR001X2101], PDR001 single-agent was administered as an intravenous infusion over 30 minutes at doses ranging from 1 to 10 mg/kg on an every 2 weeks (Q2W) schedule or at 3 and 5 mg/kg every 4 weeks (Q4W) schedules.

Approximately dose proportional increase in exposure (C1D1 AUC0- 336) was observed with doses from 1 to 10 mg/kg and no DLTs were observed.

Accumulation of approximately 2.1-3.4-fold was observed with Q2W dosing and 1.6-2.2-fold with Q4W dosing. Population PK analysis indicated that the changes in exposure due to patient weight differences are minimal across the anticipated weight range of 30 to 150 kg for the patient population. Therefore, a flat dosing scheme was selected. Based on the safety profile observed in study [CPDR001X2101] and the expected Ctrough values, 400 mg Q4W is expected to be a safe and efficacious dose. For further details on spartalizumab, please see the investigator's brochure.

#### Prior Experience with Investigational Agents

The COMBI-I study is a multicenter trial exploring the safety and efficacy of dabrafenib, trametinib and spartalizumab in patients with BRAF V600 mutated unresectable or metastatic melanoma. In Part 1 of the trial (safety run-in cohort), standard dosing of dabrafenib (150mg orally twice daily), trametinib (2mg daily) and spartalizumab (400mg IV every 4 weeks) was utilized. A total of 9 patients were enrolled and there was no excessive toxicity seen and this dosing was utilized in Part 2 which was designed to be a biomarker exploration cohort. An additional 27 patients were treated on Part 2 for a total of 36 evaluable patients for safety and efficacy. At the time of data analysis, the median follow up time was 19.9 months (16.5-25.1 months range) and treatment was ongoing for 13 patients. All patients had some form of adverse event, with 78% having experienced a grade 3 toxicity. The most common grade 3 toxicities were pyrexia (17%) and pruritus (11%). Grade 3 laboratory evaluations were noted including elevated creatinine phosphokinase (8%), amylase (8%) and gamma-glutamyltransferase (8%) levels, in keeping with prior studies. All patients required dose adjustment/interruption to mitigate toxicities and 17% of patients had toxicities leading to cessation of the triplet therapy. In terms of efficacy, the overall response rate was 78% with 42% achieving confirmed complete response, which included 20% with elevated LDH at baseline and 40% with stage IV M1c disease. The median PFS was 23.7 months, including 10.7 months for higher risk patients with elevated LDH values at time of enrollment. The median duration of response was 20.7 months with 29% of responders experiencing subsequent progression. The median overall survival was not reached in this cohort. Part 3 of this trial which is a global, placebo-controlled randomized trial of dabrafenib, trametinib and placebo vs. dabrafenib, trametinib and spartalizumab is currently in enrollment.

### 3.3.2 Dose Modification

#### ***Dose Modification of Dabrafenib and Trametinib and Spartalizumab for General Toxicities Related to Study Drug(s)***

In the event of a clinically significant grade 3 or 4 hematologic or non-hematologic AE, treatment may be withheld and supportive therapy administered as clinically indicated. If the toxicity or event resolves to baseline or Grade 1 in less than or equal to 21 days of stopping therapy, treatment may be restarted. Dose reduction should be considered as clinically indicated at the discretion of the treating oncologist. Any dose adjustment or interruption will be recorded.

If the toxicity does not resolve to at least Grade 1 in less than or equal to 21 days, withdrawal from the trial is recommended. However, if the investigator agrees that further treatment will benefit the subject, treatment can continue with a reduction of one or both study drugs.

Suggested dose reduction of each drug is as follows in Table 4. These dose reductions of dabrafenib and trametinib do not need to be made concurrently and will be up to the discretion of the treating investigator.

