**Table 4 Dose Levels**

Drug	Starting Dose	Dose level -1	Dose level -2	Dose level -3
Dabrafenib	150mg BID	100mg BID	75mg BID	50mg BID
Trametinib	2mg daily	1.5mg daily	1.0 mg daily	----- ---
Spartalizumab	400mg IV every 28 days	----- ---	----- ---	----- ---

If treatment related toxicities occur that are specific to combination treatment of dabrafenib and trametinib, then both treatments should be simultaneously dose reduced, interrupted or discontinued with the exceptions shown below:

Exception where dose modification is necessary for **only dabrafenib**:

- Uveitis  
Exception where dose modifications are necessary for **only trametinib**:
- Retinal vein occlusions (RVO) and retinal pigment epithelial detachment (RPED)
- Left ventricular ejection fraction (LVEF) reduction  
If a subject's dose of dabrafenib and trametinib has been reduced per the dose modification instructions, re-escalation of the subject's dose is recommended provided the following criteria are met:
  - a period of 4 weeks of treatment has passed since restarting dosing at the lower dose level and there is no recurrence of the AE
  - the subject is deriving clinical benefit

General dose modification guidelines are provided in Table 5

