**Table 5 Dose Modification Guidelines – General**

CTCAE Grade	Action and Dose Modification
Grade 1 or Grade 2 (tolerable)	Continue study treatments at same dose level (no dose modification)
Grade 2 (Intolerable)	
1 st or 2 nd occurrence	Interrupt study treatments until toxicity resolves to $\leq$ grade 1 then restart at same dose level
3 rd or occurrence	Interrupt study treatments until toxicity resolves to $\leq$ grade 1 then restart at next lower dose level
4 th or greater occurrence	Interrupt study treatments until toxicity resolves to $\leq$ grade 1 then restart at two dose levels lower than the starting dose or discontinue treatments per investigator discretion
Grade 3	
1 st occurrence	Interrupt study treatments until toxicity resolves to $\leq$ grade 1 or baseline then restart at next lower dose level
2 nd occurrence	Interrupt study treatments until toxicity resolves to $\leq$ grade 1 or baseline then restart at two dose levels lower than the starting dose
3 rd occurrence	Discontinue treatments.
Grade 4	
1 st occurrence	Discontinue treatments

For dabrafenib and/or trametinib related adverse events: if following an interruption of dabrafenib and trametinib, an AE doesn't recover to  $\leq$  Grade 1 or baseline within 4 weeks, dabrafenib and trametinib must be discontinued.

No dose reductions are allowed for spartalizumab. Dose interruption for spartalizumab includes delaying or withholding the treatment for any reason as well as an interruption of treatment during an infusion. All dose interruptions and the reason for the dose interruption must be recorded. Dose interruption for spartalizumab includes delaying or withholding the treatment for any reason as well as an interruption of treatment during an infusion. Subjects with adverse events suspected to be related to spartalizumab including those of potential immune-mediated etiology (irAE) must be permanently discontinued from spartalizumab if (1) the AE doesn't recover to  $\leq$  Grade 1 or baseline within 12 weeks and/or (2) the dose of steroids (for the management of irAE) remains  $> 10$  mg/day prednisone or equivalent for  $> 12$  weeks. The 12 week timeframe will begin from the time the irAE reaches a grade that leads to spartalizumab interruption.

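### The dose-modification rules conflict in four places (Grade 4 events, unresolved related events, the prednisone limit, retinal vein occlusion) and no sentence says which rule governs

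*Combined protocol and SAP*

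**What the plan says.** All references are to the combined protocol and SAP.

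- **Section 3.3.2, opening text.** "In the event of a clinically significant grade 3 or 4 hematologic or non-hematologic AE, treatment may be withheld". If the event "resolves to baseline or Grade 1 in less than or equal to 21 days of stopping therapy, treatment may be restarted". "If the toxicity does not resolve to at least Grade 1 in less than or equal to 21 days, withdrawal from the trial is recommended", but "if the investigator agrees that further treatment will benefit the subject, treatment can continue with a reduction of one or both study drugs". No outer time limit is attached to that option.
- **Section 3.3.2, Tables 4 and 5.** The text after Table 4 says "General dose modification guidelines are provided in Table 5". Table 5's entry for a first Grade 4 occurrence is to "discontinue treatments". Below Table 5, the rule for dabrafenib- or trametinib-related events that have not come down to at most "Grade 1 or baseline within 4 weeks, dabrafenib and trametinib must be discontinued" is mandatory. Spartalizumab has its own rule: permanent discontinuation if an event has not recovered within 12 weeks, or if steroids stay above 10 mg/day prednisone for more than 12 weeks. "The 12 week timeframe will begin from the time the irAE reaches a grade that leads to spartalizumab interruption".
- **Steroids elsewhere.** Section 3.7 allows spartalizumab to restart once prednisone has been tapered to 10 mg/day. Section 3.8.2 requires less than 10 mg/day before the next administration of study treatment, failing which spartalizumab must end. It names steroids given for pyrexia among those covered. Table 6 (Section 3.3.3) recommends about 10 mg prednisone for at least 5 days for pyrexia, and restarts dabrafenib and trametinib after 24 symptom-free hours.
- **RVO.** The list after Table 4 puts RVO among the events for which only trametinib is modified. Table 7 (Section 3.3.4) permanently stops trametinib at Grade 1, all study treatments at Grades 2-3, and trametinib (the only drug named) at Grade 4.

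**The concern.** These are stated rules that give different answers for the same patient, so the problem is not missing detail. Two of them bear directly on safety: a site that follows the opening text of Section 3.3.2 may re-treat after a Grade 4 event, or keep treating through an unresolved related event, where another sentence in the same section says stop. The other two affect which drugs continue. The prednisone limit helps decide whether spartalizumab resumes after an immune-related event, and spartalizumab is the drug added in the non-pCR group on which the primary objective rests. The RVO rule decides whether the partner drugs go on. Without a precedence sentence, two investigators can treat the same event differently and both cite the protocol.

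**Working it through.** The plan gives no figure on this point to reproduce. The check is to set the rules side by side, try one patient against each pair, and look for a sentence that settles the difference.

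1. **First Grade 4 event, resolved by day 14.** Opening text of 3.3.2: 14 ≤ 21 days, so restart is allowed. Table 5: discontinue, with no restart option. The rules conflict.

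2. **Dabrafenib- or trametinib-related Grade 3 event, still Grade 2 on day 29.** Opening text: past day 21, the investigator may continue at a reduced dose. Text below Table 5: 4 weeks = 28 days have passed, so both drugs must stop. The heading of the opening text limits it to toxicities related to study drug, so the two scopes overlap. Taking both clocks to start at interruption (an assumption), the rules can be nested for 28 − 21 = 7 days: withdrawal recommended at day 21, mandatory stop at day 28. After day 28 they conflict.

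3. **Prednisone and spartalizumab.**
   - Patient at exactly 10 mg/day: Section 3.7 allows restart; Section 3.8.2 does not, because 10 is not less than 10. The rules conflict.
   - Patient with pyrexia on prednisone 10 mg, symptom-free for 24 hours on day 3 of a 5-day course: Table 6 restarts dabrafenib and trametinib. Section 3.8.2 is worded for study treatment as a whole and requires less than 10 mg/day first. Following Table 6's recommendation therefore breaches Section 3.8.2.

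4. **RVO.**
   - Grade 2: the list after Table 4 modifies trametinib only; Table 7 stops all study treatments. The rules conflict.
   - Grade 4: Table 7 names trametinib only; Table 5 stops treatments at any first Grade 4 event. These also differ.

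**Search for precedence.** The text after Table 4 points to Table 5 but calls it guidelines, and does not say that it overrides the opening text. Section 3.5 announces mandatory modifications in the sections that follow, but ranks nothing. No other sentence was found that settles any of the four.

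**The case against.** The opening text of Section 3.3.2 is permissive throughout, whereas Table 5 is the grade-specific schedule and the 4-week rule is mandatory. A permission does not cancel an obligation, so a careful site following the stricter text breaches nothing. That stands, and it limits the harm. It does not remove the problem, because the opening text expressly covers Grade 4 and expressly authorises continuation, and nothing says that the stricter text wins.

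Three stronger readings are tempting, and the documents do not support them.

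- *A reader might infer that Section 3.8.2 would usually end spartalizumab after an immune-related event, because tapers outlast the 28-day dosing interval.* This needs the next dose to mean the next scheduled dose. Section 3.3.2 counts delay as a form of interruption and gives a 12-week (84-day) window, and Section 3.7 provides for restart after a taper. The scheduled-dose reading would largely empty that window. Taper length does not rescue the claim either. From an assumed 60 mg start (1 mg/kg, 60 kg), Section 3.7's 10 mg steps fall below 10 mg/day after 6 steps, 6 × 3 to 6 × 7 = 18 to 42 days. Its 2.5 mg steps need (60 − 7.5)/2.5 = 21 steps, 63 to 147 days. The result depends on the inputs chosen and can exceed 84 days. On the delayed-dose reading, what remains for spartalizumab is 10 versus less than 10 mg/day.
- *A reader might infer from Table 7 that the partner drugs are handled less strictly at Grade 4 RVO than at Grade 2.* Table 5 stops treatments at Grade 4. The defect is that the two tables differ without a ranking, not that partner drugs clearly continue.
- *A reader might infer an effect on power or the primary analysis.* None follows from these passages.

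It is also fair to object that restricting the steroid sentences of Section 3.8.2 to spartalizumab changes clinical content, since pyrexia is a dabrafenib/trametinib toxicity. But Table 6 and Section 3.8.2 cannot both stand as worded, and the penalty in Section 3.8.2 already falls on spartalizumab alone.

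**Conclusion.** The concern holds as a set of four conflicts in the current text, none resolved by a precedence rule. Cases 1 and 2 matter most, because the permissive wording can re-expose a patient whom another rule stops. Case 2 is confined to dabrafenib/trametinib-related events after day 28, assuming a common clock start. Case 3 is a boundary difference at exactly 10 mg/day, plus the clash with the pyrexia table. Case 4 concerns which partner drugs stop at RVO Grades 2-3, and an unranked difference between two tables at Grade 4.

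The documents give no Grade 4 or RVO rate, and none for unresolved related events, so how often the rules would disagree cannot be estimated. This is a matter of safety and consistent conduct, with no effect on sample size, power or the RFS test. It is worth correcting because the correction is specific and cheap.

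**What to change.** - **Section 3.3.2, opening text.** Remove Grade 4 from the withhold-and-restart sentence and state that Table 5 governs Grade 4. Cap the investigator's continuation option at 4 weeks for dabrafenib/trametinib-related events.
- **Sections 3.8.2 and 3.7.** Limit the steroid sentences of 3.8.2 to spartalizumab, which removes the clash with Table 6; the clinical team should confirm this, because it relaxes the current wording for dabrafenib and trametinib. State that the next dose may be a delayed dose within the 12-week window of Section 3.3.2. Align Section 3.7 to the stricter threshold of less than 10 mg/day. The 12-week criterion, now above 10 mg/day, should take the matching form of 10 mg/day or more, so that exactly 10 mg does not fall between rules.
- **RVO.** State that Table 7 governs, refer to it from the list after Table 4, and make its Grade 4 row at least as strict as Grades 2-3.
- **Precedence.** Add one sentence that the stricter mandatory text governs wherever dose-modification passages differ.

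The cost is a wording amendment, site retraining and slightly less investigator discretion. The sample size does not change.

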**Table 4 Dose Levels**

Drug	Starting Dose	Dose level -1	Dose level -2	Dose level -3
Dabrafenib	150mg BID	100mg BID	75mg BID	50mg BID
Trametinib	2mg daily	1.5mg daily	1.0 mg daily	----- ---
Spartalizumab	400mg IV every 28 days	----- ---	----- ---	----- ---

If treatment related toxicities occur that are specific to combination treatment of dabrafenib and trametinib, then both treatments should be simultaneously dose reduced, interrupted or discontinued with the exceptions shown below:

Exception where dose modification is necessary for **only dabrafenib**:

- Uveitis  
Exception where dose modifications are necessary for **only trametinib**:
- Retinal vein occlusions (RVO) and retinal pigment epithelial detachment (RPED)
- Left ventricular ejection fraction (LVEF) reduction  
If a subject's dose of dabrafenib and trametinib has been reduced per the dose modification instructions, re-escalation of the subject's dose is recommended provided the following criteria are met:
  - a period of 4 weeks of treatment has passed since restarting dosing at the lower dose level and there is no recurrence of the AE
  - the subject is deriving clinical benefit

General dose modification guidelines are provided in Table 5

**Table 5 Dose Modification Guidelines – General**

CTCAE Grade	Action and Dose Modification
Grade 1 or Grade 2 (tolerable)	Continue study treatments at same dose level (no dose modification)
Grade 2 (Intolerable)	
1 st or 2 nd occurrence	Interrupt study treatments until toxicity resolves to $\leq$ grade 1 then restart at same dose level
3 rd or occurrence	Interrupt study treatments until toxicity resolves to $\leq$ grade 1 then restart at next lower dose level
4 th or greater occurrence	Interrupt study treatments until toxicity resolves to $\leq$ grade 1 then restart at two dose levels lower than the starting dose or discontinue treatments per investigator discretion
Grade 3	
1 st occurrence	Interrupt study treatments until toxicity resolves to $\leq$ grade 1 or baseline then restart at next lower dose level
2 nd occurrence	Interrupt study treatments until toxicity resolves to $\leq$ grade 1 or baseline then restart at two dose levels lower than the starting dose
3 rd occurrence	Discontinue treatments.
Grade 4	
1 st occurrence	Discontinue treatments

For dabrafenib and/or trametinib related adverse events: if following an interruption of dabrafenib and trametinib, an AE doesn't recover to  $\leq$  Grade 1 or baseline within 4 weeks, dabrafenib and trametinib must be discontinued.

No dose reductions are allowed for spartalizumab. Dose interruption for spartalizumab includes delaying or withholding the treatment for any reason as well as an interruption of treatment during an infusion. All dose interruptions and the reason for the dose interruption must be recorded. Dose interruption for spartalizumab includes delaying or withholding the treatment for any reason as well as an interruption of treatment during an infusion. Subjects with adverse events suspected to be related to spartalizumab including those of potential immune-mediated etiology (irAE) must be permanently discontinued from spartalizumab if (1) the AE doesn't recover to  $\leq$  Grade 1 or baseline within 12 weeks and/or (2) the dose of steroids (for the management of irAE) remains  $> 10$  mg/day prednisone or equivalent for  $> 12$  weeks. The 12 week timeframe will begin from the time the irAE reaches a grade that leads to spartalizumab interruption.

### 3.3.3 Dose Modification Guidelines – Adverse Events of Special Interest

#### **Pyrexia**

##### **Mandatory dose modification and recommended clinical management for pyrexia syndrome suspected to be related to dabrafenib and/or trametinib treatment**

Episodes of pyrexia syndrome have been observed in subjects receiving dabrafenib monotherapy or in combination with trametinib. The pyrexia syndrome is defined as treatment-related fever ( $\geq 38^{\circ}\text{C}$ ) or chills/rigors/night sweats or flu-like symptoms. In a minority of cases the pyrexia was accompanied by symptoms such as severe rigors/chills, dehydration, hypotension, dizziness or weakness and required hospitalization. The incidence and severity of pyrexia syndrome are increased when dabrafenib is used in combination with trametinib compared to dabrafenib monotherapy.

Dabrafenib and trametinib must be interrupted promptly at the very first symptom of pyrexia or its associated prodrome (chills or rigors or night sweats or flu-like symptoms) and should be restarted upon improvement of symptoms at the same dose if symptom free at least 24 hours.

Subjects should be instructed on the importance of immediately reporting febrile episodes. In the event of a fever, the subject should be instructed to take non-steroidal anti-pyretics as appropriate to control fever. The use of oral corticosteroids should be considered in those instances in which anti-pyretics are insufficient. In subjects experiencing pyrexia associated with rigors, severe chills, dehydration or hypotension, serum creatinine and other evidence of renal function should be monitored carefully during and following severe events of pyrexia.

Pyrexia accompanied by hypotension, dehydration requiring intravenous fluids, renal insufficiency and/or severe rigors, (dehydration requiring intravenous fluids, documented infectious cause should be reported as a SAE.

Guidelines for dose modification and management for pyrexia syndrome considered to be related to dabrafenib are provided in Table 6.

**Table 6: Pyrexia Management Guidelines**

Pyrexia		
Occurrence	Recommended adverse event management guidelines	Mandatory dose modification requirements
1 st occurrence and subsequent occurrences c	
 
• Educate patient about pyrexia syndrome and to immediately interrupt dabrafenib and trametinib at the very first symptom of pyrexia or its associated prodrome (chills, rigors, night sweats or flu-like symptoms).
 
• Clinical evaluation for infection and hypersensitivity a
 
• Laboratory work-up a
 
	
 
• Dabrafenib and trametinib must be interrupted promptly at the very first symptom of pyrexia or its associated prodrome (chills, rigors, night sweats or flu-like symptoms) and should be restarted upon improvement of symptoms at the same dose if symptom free at least 24 hours.
 
• If pyrexia cannot be managed with interruption, dose reduction per
 

Pyrexia	Occurrence	Recommended adverse event management guidelines
		
 
Administer anti-pyretic treatment with non-steroidal anti-inflammatory drugs (NSAID) and/or paracetamol b
 
Recommend oral corticosteroids (i.e., prednisone 10 mg) for at least 5 days or as clinically indicated.
 
Optimize oral corticosteroid dose as clinically indicated for recalcitrant pyrexia.
 
Oral hydration should be encouraged in subjects without evidence of dehydration. Intravenous hydration is recommended in subjects experiencing pyrexia complicated by dehydration/hypotension.
 

a For subjects experiencing pyrexia, a clinical evaluation and laboratory work-up is mandatory for each event; thorough clinical examination for signs and symptoms of infection or hypersensitivity is required; laboratory work-up should include full-blood-count, electrolytes, creatinine, blood urea nitrogen (BUN), C-reactive protein (CRP), liver-function tests, blood culture, and urine culture.

b Anti-pyretic treatment should be started immediately at the first occurrence and prophylactic anti-pyretic treatment is recommended. Anti-pyretic treatment may include acetaminophen, ibuprofen, or suitable anti-pyretic medication according to institutional standards. Prophylactic anti-pyretic treatment is recommended to be discontinued after three days in the absence of pyrexia.

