## 1.2 MODERN NEOADJUVANT TRIALS

### *Dabrafenib plus trametinib*

There are two mature studies evaluating the combination of dabrafenib (150 mg twice daily) and trametinib (2 mg daily) in the neoadjuvant setting.

In the Combi-Neo trial (MD Anderson Protocol 2014-0409; NCT02231775), patients with stage IIIB/C (AJCC 7th edition) or oligometastatic stage IV *BRAF*-mutant melanoma were randomized to either surgery followed by standard of care adjuvant therapy (which could be observation alone, high dose interferon, pegylated IFN- $\alpha$ 2b, high-dose ipilimumab, or biochemotherapy) or neoadjuvant combination dabrafenib and trametinib (8 weeks) followed by 44 weeks postoperatively. Interim analysis of the initial 21 patients enrolled demonstrated that neoadjuvant dabrafenib and trametinib was associated with a high imaging response rate (77%) and pCR rate of 58%. At a median follow-up of 18.6 months, neoadjuvant targeted therapy was associated with significantly better RFS than patients randomized to surgery followed by possible postoperative adjuvant therapy (HR 60.2, 95% CI 6.7-7965, p<0.0001).

There was also improved distant metastasis-free survival (HR 0.024, p=0.001) and trend towards improved overall survival (HR 0.28, [=0.22) for the neoadjuvant dabrafenib and trametinib treated patients. Of note, pCR patients had a trend towards improved relapse free survival and overall survival compared to the upfront surgery patients and did have statistically significant improvement in distant metastasis-free survival over non-pCR patients; indicating that pathologic responses can influence patient survival outcomes.

This regimen also showed a manageable safety profile for dabrafenib and trametinib, similar to that observed in patients with metastatic melanoma, with pyrexia and chills as the most commonly reported adverse events (AEs), none of which interfered with the ability to carry out planned surgery. There were no progression events during the neoadjuvant treatment and all patients were able to proceed to surgical intervention.

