### **3.8.2 Prohibited Concomitant Medications**

The use of systemic steroid therapy and other immunosuppressive drugs is not allowed except for the treatment of infusion reaction, irAEs, and for prophylaxis against imaging contrast dye allergy or replacement-dose steroids in the setting of adrenal insufficiency (providing this is <10 mg/day prednisone or equivalent), or transient exacerbations of other underlying diseases such as COPD requiring treatment for  $\leq$  3 weeks. If systemic corticosteroids are required for the control of infusion reactions, pyrexia or irAEs, it must be tapered and be at non-immunosuppressive doses (< 10 mg/day of prednisone or equivalent) before the next administration of study treatment.

If the dose of prednisone or equivalent cannot be reduced to less than 10 mg/day before the administration of next dose of study treatment then spartalizumab must be discontinued.

The use of live vaccines is not allowed through the whole duration of the study. Inactivated vaccines are allowed.

Dabrafenib induces CYP3A4- and CYP2C9- mediated metabolism and may induce other enzymes including CYP2B6, CYP2C8, CYP2C19 and UDP glucuronosyltransferases (UGT). Dabrafenib may also induce transporters (e.g., P-glycoprotein (P-gp)). Co-administration of dabrafenib and medicinal products which are affected by the induction of CYP3A4 or CYP2C9 such as hormonal contraceptives, warfarin or dexamethasone may result in decreased concentrations and loss of efficacy. If co-administration of these medications is necessary, monitor subjects for loss of efficacy or consider substitutions of these medicinal products. Use caution if co-administration of CYP2C or CYP3A4 substrates with narrow therapeutic index is required. Refer to the dabrafenib label for further information.

Based on *in vitro* and *in vivo* data, trametinib is unlikely to significantly affect the pharmacokinetics of other medicinal products via interactions with CYP enzymes or transporters.

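### Section 3.3.3, Table 6 and Section 3.8.2 do not agree on steroids for pyrexia, and the Table 6 dose does not meet the Section 3.8.2 limit if a study drug falls due during the course

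*Combined protocol and SAP*

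**What the plan says.** Three places in the protocol govern steroids for pyrexia.

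- **Section 3.3.3, Pyrexia (text):** "The use of oral corticosteroids should be considered in those instances in which anti-pyretics are insufficient". No dose or duration is given. On restarting dabrafenib and trametinib after the interruption, the text says that they "should be restarted upon improvement of symptoms at the same dose if symptom free at least 24 hours". The mandatory column of Table 6 repeats this.
- **Table 6, recommended column:** "Recommend oral corticosteroids (i.e., prednisone 10 mg) for at least 5 days or as clinically indicated". The row label covers the first "occurrence and subsequent occurrences". A separate bullet deals with adjusting the steroid dose for recalcitrant fever. The row carries a footnote c whose wording is not in the text available to this review.
- **Section 3.8.2:** "The use of systemic steroid therapy and other immunosuppressive drugs is not allowed except for the treatment of infusion reaction, irAEs", followed by a few further uses, none of which is pyrexia. The next sentence names pyrexia, with infusion reactions and irAEs, as a reason for systemic steroids. It requires a taper to below 10 mg/day of prednisone or equivalent before the next administration of study treatment. The trigger then reads "If the dose of prednisone or equivalent cannot be reduced to less than 10 mg/day before the administration of next dose of study treatment", and the consequence is that spartalizumab must be discontinued.

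**The concern.** Pyrexia will be met often. Section 1.2 names it, with chills, as the most commonly reported adverse event on neoadjuvant dabrafenib and trametinib. Section 3.3.1 reports it as the most common grade 3 toxicity on the triplet, at 17%. These are therefore rules that sites will use repeatedly.

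The places differ on when steroids are given. They also differ on whether pyrexia is a permitted reason, and on the dose that may be running when a study drug is next taken. The last difference carries a consequence for spartalizumab, the drug whose addition is under test in the non-pCR patients. Those patients carry the primary 12-month RFS comparison (Section 7.0, planned on 24 of them). Sites that resolve the conflict differently would give different steroid exposure, and possibly different spartalizumab exposure, for the same event.

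**Working it through.** The protocol states no figure to reproduce. The check sets the rules side by side and adds simple counting.

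**1. When steroids are used.**

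| Place | Condition | Strength |
|---|---|---|
| Section 3.3.3 text | anti-pyretics insufficient | consider |
| Table 6 | any occurrence, as the row is labelled | recommend |
| Section 3.8.2, permitted list | pyrexia not listed | not allowed outside the list |
| Section 3.8.2, next sentence | steroids required to control pyrexia | contemplated, with taper |

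The first two rows differ in condition and strength. The last two are inconsistent within one paragraph.

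**2. Dose against limit.** Table 6 gives 10 mg, read here as a daily dose because no frequency is stated. Section 3.8.2 requires strictly less than 10 mg/day. Since 10 is not below 10, a study-treatment dose given while the Table 6 dose is running does not meet Section 3.8.2.

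**3. What counts as study treatment.** Section 3.8.2 does not define it, and usage elsewhere varies. Sections 3.3.4 and 3.3.9 use the term in connection with trametinib and dabrafenib. Table 5 uses the plural for the drugs together. Section 3.6.2 uses it for the infusion.

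*3a. If it includes dabrafenib and trametinib.* Suppose the steroid starts at time 0 and runs for 5 days, and symptoms clear after s days. Restart is possible from day s + 1, so the overlap with the course is 5 − (s + 1) = 4 − s days. The documents give no value for s, so a range is shown:
- s = 1: 3 days
- s = 2: 2 days
- s = 4: none

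For any fever that clears within 4 days, restarting at the earliest permitted time falls inside the course.

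*3b. If it means spartalizumab only.* Infusions are every 28 days (Table 2c). Assume that fever onset is uniform over the interval and the course lasts L days at 10 mg.
- Share of start days whose course includes an infusion day = L/28.
- L = 5: 5/28 = 17.9%. The other 23/28 = 82.1% finish before the next infusion.
- L = 10 (an illustration, since Table 6 sets a minimum): 10/28 = 35.7%.

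Table 12, note i, allows ±7 days. If the infusion is due on day d of the course and waits for the first day after it, the delay is L + 1 − d days.
- L = 5: the longest delay, at d = 1, is 5 days, which is inside the window.
- L = 10: d = 1, 2 and 3 need 10, 9 and 8 days, which are outside it. That is 3/28 = 10.7% of start days.

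**4. The stop.** Section 3.8.2 requires spartalizumab to be discontinued if the dose *cannot be reduced* below 10 mg/day by the next dose. Being on a Table 6 course is not in itself an inability to reduce it.

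**The case against.** The case for leaving the text alone has real strength.

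- **The spartalizumab-only reading is defensible.** The consequence falls on spartalizumab alone, and Section 3.6.2 uses study treatment for the infusion. Counting every daily dabrafenib or trametinib dose would also sit badly with two irAE rules: Section 3.3.2 stops spartalizumab only after more than 12 weeks above 10 mg/day, and Section 3.7 lets it restart once the taper reaches 10 mg/day. This stands as an argument about likely intent. It does not settle the term, because the trigger sentence uses study treatment and spartalizumab as if they were different things.
- **The overlap is then small and has an outlet.** For a 5-day course this stands: the visit window covers it, and Section 3.3.2 treats a delay as an interruption, separate from discontinuation. It is weaker for a longer course, which Table 6 allows.
- **Section 3.3.3 and Table 6 are both advisory.** The text refers the reader on to Table 6, and footnote c may qualify the row. This stands. The two differ in condition and strength; neither forbids what the other advises.
- **Section 3.8.2, read whole, does contemplate steroids for pyrexia.** Probably so. A reader might infer an outright ban from the permitted list, but the next sentence does not support one. The list still needs to agree with that sentence.

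A reader might also infer that the recommended course would by itself permanently stop spartalizumab. The documents do not support this. The trigger is inability to reduce the dose, Table 6 allows the course to be adjusted as clinically indicated, and Section 3.8.2 does not say that the stop is permanent. Other places, such as Table 7 and Table 9, use that word where they intend it.

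**Conclusion.** The inconsistency is real. As written, Table 6 and Section 3.8.2 cannot both be met when a study-treatment dose falls due while prednisone is at 10 mg/day. Section 3.8.2 is also inconsistent with itself on whether pyrexia is a permitted use.

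The size depends on an undefined term. With dabrafenib and trametinib included, the conflict arises whenever they restart during the course. With spartalizumab only, it arises for about 18% of start days for a 5-day course, assuming uniform onset, and the visit window may remove it. Spartalizumab could have to be discontinued, but only where the dose cannot be brought below 10 mg/day in time.

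The number of patients affected cannot be estimated. A reader might take 17% of 24, about 4 patients, as that number. It counts grade 3 pyrexia, not patients whose steroid dose is still at 10 mg/day or more and cannot be lowered when a dose is due. The documents give no all-grade rate and no course durations. A reader might likewise infer a distorted primary RFS result; nothing in the documents shows the direction or size of such an effect. The point is one of consistent conduct, safety and drug exposure, and it should be corrected on those grounds.

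**What to change.** Reconcile Section 3.3.3, Table 6 (including footnote c) and Section 3.8.2 so that:

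1. one statement says when steroids are used for pyrexia;
2. the permitted-use list in Section 3.8.2 agrees with that statement;
3. the Section 3.8.2 dose threshold and the Table 6 course are compatible;
4. Section 3.8.2 names the drug or drugs meant by study treatment, both in the taper requirement and in the discontinuation trigger.

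The clinical team decides which rule stands; this review takes no position on it. The cost is a wording amendment. The sample size and the analysis are unaffected. No new data collection is needed to describe steroid courses and spartalizumab interruptions, because Section 3.8.1 already requires drug, dose and dates for concomitant medication, and Section 3.3.2 already requires interruptions and their reasons to be recorded.
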